PREG2 protocol synopsis

Name	PREG2					
Title	PRE vention of intrauterine adhesion after adhesiolysis with novel tri-block de G radable polymer film. NCT04963179.					
Protocol version date	December 16th 2022					
Rationale for study	PREvention of intrauterine adhesion after adhesiolysis with nove tri-block deGradable polymer film. NCT04963179. December 16th 2022 Intrauterine adhesions (IUA) are defined as "fibrous strings at opposing walls of the uterus and/or cervix leading to partial or complete obliteration of the cavity" ¹ . IUA can lead to recurrent pregnancy loss infertility, abnormal placentation, menstrual abnormalities, and pain. ^{1,7} Treatment by hysteroscopic lysis is recommended if the patient has clinical symptoms. However, one of the greatest challenge is the recurrence of adhesive disease ^{1,3} : the recurrence rate after intrauterine synechiae lysis is 20% to 32% and 42% to 60% in the case of severe synechiae lysis is 20% to 32% and 42% to 60% in the case of severe synechiae lysis is 20% to 32% and recurrences makes reproductive outcomes unsatisfactory, even after hysteroscopic treatment ⁸ . It is acknowledged that the use of an intrauterine barrier potentially reduces postoperative adhesion reformation. However, existing barriers have suboptimal efficacy due to their limited residence time in the uterus (HA gel) or need of manual removal (IUD, balloon, amnior graft). As a result, a golden standard to prevent adhesive disease does not exist. Therefore, there is an unmet medical need for an evidence based effective secondary prevention method. Hence the evaluation of the efficacy of the anti adhesion effects of Womed Leaf after adhesiolysis. Name : Womed Leaf Device group : Anti-adhesion barrier					
Study device						

¹ Hooker et al., Prevalence of intrauterine adhesions after the application of hyaluronic acid gel after dilatation and curettage in women with at least one previous curettage: short-term outcomes of a multicenter, prospective randomized controlled trial. Fertility and Sterility. 2017;107(5):0015-0282.

² Tuuli MG et al. Uterine synechiae and pregnancy complications. Obstet Gynecol 2012 ; 119 :810-4

³ Warembourg S et al. Prevention and treatment of intrauterine synechiae : Review of literature. J Gynecol Obstet Biol Reprod. 2015 Apr ; 44 :366-79.

⁴ Pabuccu 1999

Randomization	Computer generated randomization in 1:1 ratio Randomization will be stratified by IUA severity (moderate/severe) determined at the beginning of adhesiolysis.			
Primary effectiveness endpoint	The primary effectiveness endpoint is: Change of AFS score between pre-adhesiolysis and second-look hysteroscopy (AFS) score.			
Primary safety endpoint	The primary safety endpoint is: Adverse events up to second look hysteroscopy (6 weeks +/- 2 weeks).			

⁹ AAGL practice report: practice guidelines on intrauterine adhesions developed in collaboration with the European Society of Gynecological Endoscopy (ESGE), 2017

٦

Key Secondary Effectiveness Endpoints Other secondary	 1. 2. 3. 4. 5. 6. 7. 8. 	High-responder rate i.e: percentage of patients who have improved from severe to mild adhesions or from severe to no adhesions or from moderate to no adhesions at second look Change of "extent of cavity involved", according to the 10-zone uterine diagram, between pre-adhesiolysis and second-look hysteroscopy Change in "extent of cavity involved" component between post-adhesiolysis and second look hysteroscopy AFS scores at second look hysteroscopy Extent of IUA AFS score component Type of IUA AFS score component Menstrual pattern AFS score component Percentage of patients who have Mild adhesions or no adhesion at second look
endpoints		
	1.	Freedom from IUA (rate) at second look hysteroscopy (6 weeks +/- 2 weeks)
	2.	ESGE stage at second look hysteroscopy
	3.	Level of post-operative pain on a numeric rating scale, with $0 = no pain and 10 = the worst pain.$
	4.	Level of discomfort related to vaginal discharge on a numeric rating scale, with $0 = no$ discomfort and $10 = extremely$ disturbing.
	5.	Timing of vaginal discharge as recalled by the patient
	6.	Duration of the vaginal discharge
	7.	Qualitative description of the vaginal discharge
	8.	Change of menstrual pattern at second look hysteroscopy, 1 year and 2 years
	9.	Reintervention rate, during second look hysteroscopy or scheduled later up to one year
	10.	Number of adhesiolysis procedures after second look up to one year
	11.	Pregnancy rate defined as presence of foetal sac or heartbeat by ultrasound at 1 year and 2 years, whether spontaneous or IVF
		Live birth rate at 1 year and 2 years
		Pregnancy complication rate
	14.	Time to pregnancy (i.e. time between the second look hysteroscopy and pregnancy start)
	15.	IUA severity according to Chinese scoring system (for patients enrolled in China only)
	16	Responder rate: Percentage of patients with an improvement of
	10.	one clinical category i.e from Severe to Moderate or from Moderate to Mild
Inclusion criteria	1.	Women with moderate or severe intrauterine adhesions according
		to the AFS classification, i.e AFS score >=5, confirmed by
		hysteroscopy right before adhesiolysis
	2.	Scheduled for hysteroscopic adhesiolysis
	3.	Age above or equal to 18
	J.	

Exclusion criteria	 Subjects who can comply with the study follow-up (second look hysteroscopy) and other study requirements. Subjects who agree to refrain from intercourse or use a reliable form of barrier contraception to prevent unintended pregnancy until the follow-up hysteroscopy. Subjects who agree to avoid all intrauterine devices (IUDs) until the follow-up hysteroscopy. Pre-operative criteria Post menopause Pregnant (confirmed by a positive pregnancy test) or lactating Abnormal uterine cavity according to ESHRE classification I to V such as unicornis, bicornis, septate, duplex Known or suspected endometrial hyperplasia History of cervical or endometrial cancer Active pelvic infection or history of pelvic peritonitis History of endometrial ablation Known contraindication or hypersensitivity to Womed Leaf component Current participation in another clinical investigation that has not yet received the primary endpoint. Any other condition that makes participation in the study contrary to the patient's best interests. Intra-operative criteria, post adhesiolysis: Perforation during adhesiolysis Uterine depth < 5cm or > 10cm 					
Intervention technique	Hysteroscopic adhesiolysis using tools according to local practice of the participating center.					
Procedure and drug regimen	According to local practice of the participating site					
Data collection and Follow up schedule	 Assessment of IUA severity at the beginning and at the end of operative hysteroscopy Assessment of procedure or device related adverse event at 2 weeks and 6 weeks Second-look hysteroscopy at 6 weeks (+/-2 weeks) to assess recurring IUA. All patients will be contacted at 1 year and 2 years (+/- 1 month) by email and/or phone call to assess their pregnancy status. See table below. 					
Timelines	The first patient will be included in Q4 2021. Patient inclusion will last 24 months. Evaluation of the primary outcome will be done by Q1 2024. Total study duration (including long term follow-up): 4 years Data gathering and analysis before manuscript submission: 3 months.					

Blinding	Open label to the surgeon Blinded to the study subjects and the hysteroscopy evaluator.				
Sample Size Calculation	 Two sided test Confidence interval: 95% (5% alpha/type I error) Power: 90% (10% beta/type II error) Hypothesis*: Control group: mean difference of AFS score = 5 Study group: mean difference of AFS score = 6 Standard deviation: 1,8 ⇒ Sample size: 138 Loss to follow up: 10% ⇒ Total population: 154 subjects with a 1:1 randomization 				
Statistical Analysis Plan	The Intention To Treat (ITT) population is defined by all randomized patients. The safety population is defined by all randomized patients. Standard descriptive statistics will be used. Randomization being stratified on IUA severity, statistical analysis will be adjusted on IUA severity. For the primary effectiveness endpoint (classification of adhesions): A covariance analysis (ANCOVA) with the mean change of AFS score between pre-adhesiolysis and SLH as dependent parameter, with IUA severity stratum as covariate will be conducted to compare the 2 groups. The two-sided 95% Cl of the mean change of AFS score between pre-adhesiolysis and SLH will be estimated independently in each randomization group using standard error (SE). If H0 is rejected and $\Delta_{WOMED} > \Delta_c$ then, superiority of Womed Leaf over no IUA prevention method will be concluded. If the normality of the change of AFS score cannot be assumed, the tertiles of the parameter will be used as a dependent parameter and an ordinal logistic regression model will be used. For the primary safety endpoint, all AE will be presented. For key secondary efficacy endpoints: The list of key secondary endpoints has been hierarchically ordered. For each endpoint, the hypotheses will be tested using a fixed-sequence method following the order defined, using 2-sided statistical tests, all at the same significance level alpha ($\alpha = 0.05$), moving to a second endpoint only after a success on the previous endpoint.				
Applicable Norms	ISO 14155:2020, Good Clinical Practice, 21 CFR Parts 11, 50, 54, 56, and 812, Medical Device Regulation (EU) 2017/745 (MDR) and MDCG 2020-10/1 guidance, Good Clinical Practice for Medical Devices Clinical trials (Decree No. 28, 2022) promulgated by NMPA in 2022.				

		D-7 days (±7days)	D0		2 weeks (+/-1 week)	6 weeks (+/-2 weeks)	1 year (+/-1 month)	2 years (+/-1 month)
Data / imaging collection	Enrollment	Pre-operativ e visit		After adhesiolysis	Phone call	Second look HSC	Phone call and/or email	Phone call and/or email
Patient information	х							
Inclusion criteria validation	x		х	x				
Informed consent*	Х							
Pregnancy test	х							
Medical History		Х						
Baseline characteristics		x						
Uterine depth				х				
AFS score			х	х		х		
Presence and location of IUA (diagram)				x		х		
Hysteroscopy recordings (not mandatory)			х	x		x		
Intervention report				х		х		
Device performance related event				х				
Adverse events (AE)				х	х	х		
Medication		х		х	х	х	х	х
Menstrual pattern		х				х	х	х
Patient reported outcomes						х	х	x
Pregnancy status (and date)						x	х	х
Live birth							х	х
Pregnancy complications							х	x

Data collection and follow-up table

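### Fertility endpoints are followed in all patients, but wish to conceive is neither an eligibility criterion, a named data item nor part of any stated analysis set, so the absolute comparison is diluted

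*Combined protocol and SAP*

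**What the plan says.** The Design section sets follow-up at 6 weeks for the primary endpoint and 2 years for fertility. Among the other secondary endpoints is "Pregnancy rate defined as presence of foetal sac or heartbeat by ultrasound at 1 year and 2 years, whether spontaneous or IVF". The same list includes the live birth rate at those two times and time to pregnancy, counted from second look. None of the three has a stated denominator, and time to pregnancy has no censoring rule.

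Eligibility rests on an AFS score of at least 5, planned adhesiolysis, age 18 or over, not being post-menopausal, ability to comply with follow-up, and safety exclusions. The criteria that touch on reproductive behaviour concern only the weeks before second look: avoiding pregnancy, and "Subjects who agree to avoid all intrauterine devices (IUDs) until the follow-up hysteroscopy". Nothing concerns the wish to conceive afterwards.

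The follow-up schedule has every patient contacted at 1 and 2 years about pregnancy. The data collection table has rows for pregnancy status and date, live birth and pregnancy complications. It has no row for pregnancy wish, attempts to conceive or contraception after second look. The Statistical Analysis Plan section states: "The Intention To Treat (ITT) population is defined by all randomized patients". It defines no other effectiveness population.

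**The concern.** The Rationale names pain and menstrual abnormalities as well as infertility and pregnancy loss as consequences of adhesions, and recommends lysis when there are clinical symptoms. Women treated for reasons other than fertility are therefore eligible, and after second look nothing in the criteria restricts contraception. In an all-randomized analysis their lack of pregnancy looks the same as failure to conceive.

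The fertility rates would then mix biology with choice, the absolute difference would be smaller than among women trying, and precision would be lost. Timing makes this more than missing detail. A wish not recorded before randomization cannot be cleanly recovered later, because an answer given after second look may depend on what the hysteroscopy showed, and that is itself an outcome of treatment.

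**Working it through.** **1. The plan's own sample size.** Inputs from Sample Size Calculation: "Two sided test", alpha 5%, power 90%, SD 1.8, "Control group: mean difference of AFS score = 5" and "Study group: mean difference of AFS score = 6", so the difference is 1.

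n per arm = 2 × [1.8 × (1.960 + 1.282) / 1]² = 68.1, rounded up to 69, or 138 in total. With 10% loss, 138 / 0.9 = 153.3, rounded up to 154, or 77 per arm. Both stated figures reproduce. They size the AFS endpoint only; the plan gives no expected rate or power for fertility.

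**2. Dilution.** Let w be the share of women trying to conceive and p the pregnancy rate among them. If women not trying have no pregnancies, the all-randomized rate is w × p. The absolute difference is then w × (p₁ − p₀), while the relative risk stays at p₁/p₀. The documents give neither w nor p, so **every w and p below is an assumption**.

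**3. Scenario A: 40% control vs 60% study among women trying, 77 per arm.** Power = Φ[(d − 1.96 × SE₀)/SE₁], with SE₀ from the pooled rate and SE₁ from the separate rates.

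Example, w = 0.7:
- All randomized: 28% vs 42%, d = 0.14, SE₀ = √(2 × 0.35 × 0.65/77) = 0.0769, SE₁ = √[(0.28 × 0.72 + 0.42 × 0.58)/77] = 0.0760. Power = Φ(−0.14) = 44%.
- Women trying only: n = 0.7 × 77 = 53.9 per arm, d = 0.20, SE₀ = √(2 × 0.5 × 0.5/53.9) = 0.0963, SE₁ = √(0.48/53.9) = 0.0944. Power = Φ(0.12) = 55%.

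| w | All randomized | Difference | Power, all | Power, women trying |
|---|---|---|---|---|
| 1.0 | 40% vs 60% | 20 points | 70% | 70% |
| 0.9 | 36% vs 54% | 18 points | 61% | 66% |
| 0.8 | 32% vs 48% | 16 points | 53% | 60% |
| 0.7 | 28% vs 42% | 14 points | 44% | 55% |
| 0.5 | 20% vs 30% | 10 points | 30% | 42% |

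The relative risk is 1.50 in every row. If women not trying had a 2% pregnancy rate, it would be 1.48 to 1.50. Before rounding, the cost in power is about 4 to 12 points for w from 0.9 to 0.5.

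**4. Scenario B: 30% vs 55% among women trying, 69 per arm.** Power = Φ(d/SE₁ − 1.96).

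| w | All randomized | Power, all | Power, women trying |
|---|---|---|---|
| 0.8 | 24% vs 44% | 72% | 78% |
| 0.6 | 18% vs 33% | 54% | 66% |
| 0.4 | 12% vs 22% | 35% | 49% |

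The cost is about 6 to 14 points. With the pooled formula of step 3 it is about 6 to 12.

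**5. Sensitivity.** The cost depends on the assumed rates. With step 3's formula and 77 per arm, 30% vs 50% gives 3 to 9 points, and 30% vs 45% gives 2 to 5, for w from 0.9 to 0.5.

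**6. Chance imbalance in w.** The SD of the between-arm difference in w is √[2w(1 − w)/77]: 0.064 at w = 0.8 and 0.081 at w = 0.5. The 95% range is therefore about ±13 to ±16 points. Without a baseline record this can be neither inspected nor adjusted for.

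**The case against.** A reader might infer that women are never asked about wishing to conceive, and that each woman who chooses not to is counted as a device failure. The documents do not support either statement. They are a synopsis without case report forms. The rows for medical history, baseline characteristics and patient reported outcomes are open-ended, and the medication row runs to 2 years and could show hormonal contraception. What can be said is that the item is not named and no analysis uses it. The failure reading also goes too far: the all-randomized population is defined but not expressly assigned to the fertility endpoints. For time to pregnancy, women not trying would more likely be censored than failed, though they would still sit in the risk set.

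A reader might also infer bias. Randomization makes any imbalance in pregnancy wish non-systematic, and ordinary standard errors already allow for it. It is lost precision.

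The power figures describe a test the plan does not state. These endpoints lie outside the fixed sequence, carry no hypothesis, and fall under a general promise of descriptive statistics. The assumed rates are not from the documents, and the 69 per arm in scenario B is the evaluable number at 6 weeks, not at 2 years. Even with every woman trying, scenario A has only about 70% power. An all-randomized pregnancy rate is also a legitimate quantity to report.

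All of this stands, and it limits the size of the point. It does not remove the gap: as written, the plan does not secure the record needed to interpret the fertility results.

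**Conclusion.** The point holds as a worthwhile, inexpensive improvement to the secondary fertility endpoints. On the plan as written, choice and failure to conceive cannot be separated, and the absolute difference shrinks by the factor w. The illustrative cost is about 4 to 14 power points across scenarios A and B, less with the lower rates in the sensitivity check. These figures assume that women not trying have no pregnancies and that baseline wish matches later attempts. Some women will change their minds, so the gain from a set defined by baseline wish would be somewhat smaller. The relative risk is roughly preserved, no systematic bias between arms arises, and the primary and key secondary conclusions do not depend on this.

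**What to change.** Add one item at the pre-operative visit: wishes to conceive within 2 years, yes or no. Severity for stratification is determined at the start of adhesiolysis, so this visit precedes randomization and the subset it defines remains a randomized comparison. Report pregnancy rate, live birth rate and time to pregnancy in women who answered yes, alongside the all-randomized result. State the denominator for each rate and the censoring rule for time to pregnancy. At the existing 1- and 2-year contacts, ask about attempts to conceive and contraception, for description only, since those answers follow treatment.

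This version is dated December 2022, and inclusion was planned to run 24 months from Q4 2021, so about half of that window had passed. For patients already enrolled, use the wish only where it was documented before randomization, and state how many have no record. Those women stay in the all-randomized analysis.

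The cost is one baseline question, one question at contacts already planned, and a few lines of analysis plan. The downside is a smaller fertility set. For patients enrolled before the change, baseline wish will be incomplete and membership of the set will depend on what the notes happen to record, so the all-randomized result must remain beside it.

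### Does the follow-up bullet on procedure- or device-related adverse events narrow what is collected for the primary safety endpoint?

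*Combined protocol and SAP*

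**What the plan says.** Four places in the combined protocol and SAP bear on which adverse events are collected up to the second look.

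- **Data collection and Follow up schedule** (synopsis): "Assessment of procedure or device related adverse event at 2 weeks and 6 weeks". The same cell ends with "See table below".
- **Primary safety endpoint**: "Adverse events up to second look hysteroscopy (6 weeks +/- 2 weeks". There is no reference to relatedness.
- **Statistical Analysis Plan**: "For the primary safety endpoint, all AE will be presented". The safety population is every randomized patient.
- **Data collection and follow-up table**: a row labelled "Adverse events (AE", again with no relatedness limit. It is marked after adhesiolysis, at the 2-week phone call and at the 6-week second look.

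No passage explains the qualifier in the bullet, and none says that unrelated events are to be left out.

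**The concern.** Adverse events are the primary safety endpoint, so the rule for what is recorded should match what is to be reported. The bullet attaches a relatedness qualifier to the 2-week and 6-week assessments, and these are the only scheduled adverse event contacts after the operating day. If a site took the qualifier as a condition for entry, events judged unrelated would never reach the database. No analysis could restore them, and the promise to present all adverse events could not be kept. With at least 7 centers planned, two readings of one instruction could also lead to uneven recording between sites.

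It is natural to ask as well whether the arms could be affected differently, since the surgeon knows the allocation and controls receive no device.

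**Working it through.** The plan states no figure on this point, so the check sets the passages side by side. The sample size rests only on AFS score changes (means of 5 and 6, standard deviation 1.8) and 10% loss to follow-up. No adverse event rate enters it.

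**Step 1. Scope in each place.**

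| Place | Relatedness limit? | Timing |
|---|---|---|
| Primary safety endpoint | None | Up to second look |
| Statistical Analysis Plan | None (all events) | That of the endpoint |
| Follow-up table, adverse event row | None | After adhesiolysis, 2 weeks, 6 weeks |
| Follow-up schedule bullet | Procedure or device related | 2 weeks, 6 weeks |

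Three of the four statements set no limit, and those three agree with one another.

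**Step 2. Can all four be followed at once?** Yes. Related events are a subset of all events. A site that records every adverse event at the three marked contacts, and notes its relationship to procedure or device, satisfies the endpoint, the analysis, the table and the bullet. A true contradiction would need the bullet to exclude unrelated events, and it does not say so.

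**Step 3. Is the cell a complete specification?** No. For the 1- and 2-year contacts it says only that patients are reached "by email and/or phone call to assess their pregnancy status". The table marks 6 rows at each of those contacts: medication, menstrual pattern, patient-reported outcomes, pregnancy status, live birth, and "Pregnancy complications". The cell therefore names 1 of 6 and leaves 6 − 1 = 5 to the table. It also leaves out the adverse event assessment marked after adhesiolysis: the table has 3 adverse event marks and the bullet names 2. The cell is a summary, and the table is the detailed schedule to which it refers.

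**Step 4. What is lost?** If the table is followed, nothing. If the bullet were applied as an entry rule, 2 of the 3 scheduled adverse event assessments would be narrowed. That counts contacts, not events. The documents give no adverse event rate and no share of events judged unrelated, so no number of lost events can be derived.

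**Step 5. Could the arms differ?** The blinding entry reads "Open label to the surgeon Blinded to the study subjects and the hysteroscopy evaluator". Both arms undergo adhesiolysis, so procedure-related events can occur in both. Subjects do not know their allocation, and the documents do not say who judges relatedness. A difference in capture between arms is conceivable under the restrictive reading, but nothing in the documents shows one.

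**The case for a change.** The strongest argument for a change is that leaving something out differs from qualifying it. A reader sent to the table can fill in the items that the cell omits without meeting any conflict. The adverse event bullet instead adds a condition that the table row lacks, and no passage says which text prevails. The table also keeps device performance events in a separate row, so its general adverse event row is not shorthand for device-related events. Unrecorded events cannot be recovered, and a rewording would cost almost nothing.

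Part of this stands. The qualifier is unexplained, and the comparison with the shortened 1- and 2-year bullet is not exact. But the distinct device row supports reading the adverse event row as unrestricted, which is the reading that protects the endpoint. For harm to follow, a site would have to work from one synopsis bullet, disregard the table to which its cell points, and add an exclusion that the bullet does not state. A low cost of rewording does not create a benefit: new wording would only repeat what the endpoint, the analysis and the table already require.

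**Conclusion.** No change to the plan is needed. The bullet is loosely worded, and this is a clerical slip in a summary cell. The endpoint, its analysis and the collection schedule agree on unrestricted adverse events, and the cell itself leads the reader to that schedule. The expected effect is zero lost events when the table is followed, with no consequence for any effectiveness result, the sample size, power or the fixed testing sequence. No bias between arms is shown.

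This rests on one assumption: that sites and the case report form work from the follow-up table. The document is a synopsis, and neither the form nor any fuller adverse event instructions are included, so this cannot be confirmed here. If those materials limited entry to related events, the primary safety endpoint could not be reported as planned and the conclusion would differ. Nothing in the documents supplied suggests that they do.

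### The primary ANCOVA adjusts for the moderate/severe stratum but not for the pre-adhesiolysis AFS score already collected: valid, but possibly less precise than it could be

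*Combined protocol and SAP*

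**What the plan says.** The primary effectiveness endpoint is "Change of AFS score between pre-adhesiolysis and second-look hysteroscopy (AFS) score". Under Statistical Analysis Plan it is analysed by ANCOVA "with the mean change of AFS score between pre-adhesiolysis and SLH as dependent parameter, with IUA severity stratum as covariate will be conducted". The stratum is the two-level moderate/severe factor used in the randomisation. The same section says generally that analyses are adjusted for severity because the randomisation was stratified on it.

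If normality cannot be assumed, "the tertiles of the parameter will be used as a dependent parameter and an ordinal logistic regression model will be used"; no covariates are listed in that sentence.

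The baseline score is available. The follow-up schedule includes "Assessment of IUA severity at the beginning and at the end of operative hysteroscopy", and the data collection table marks the AFS score at D0 in the column before the post-adhesiolysis one. The endpoint cannot be computed without it. No section puts the score itself into the primary model, the fallback or a sensitivity analysis.

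**The concern.** The baseline score is one of the two components of the outcome. Patients enter with an AFS score of 5 or more, so scores can differ within each severity stratum. Unless the second-look score rises one-for-one with baseline inside a stratum, the change is related to baseline there, and a two-level factor cannot remove that relation.

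Two things follow. The residual variance, and so the confidence interval for the treatment effect, is wider than it need be. And in any one trial, a chance within-stratum imbalance in baseline between arms moves the estimate by the imbalance times the slope of change on baseline. What is at stake is precision and power, not bias over repeated randomisations and not type I error.

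**Working it through.** **1. The plan's own sample size.** Inputs from Sample Size Calculation: "Two sided test"; "Confidence interval: 95% (5% alpha/type I error"); "Power: 90% (10% beta/type II error"); mean changes 5 and 6, so a difference of 1; "Standard deviation: 1,8"; 1:1 allocation; 10% loss to follow-up.

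n per arm = 2 × (1.960 + 1.282)² × 1.8² / 1² = 2 × 10.507 × 3.24 = 68.1, rounded up to 69, so 138 in total. 138 / 0.9 = 153.3, rounded up to 154. Both stated figures reproduce. With the t distribution, power at 69 per arm is 90.0% (90.4% by the normal formula).

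**2. What baseline adjustment removes.** Let *b* be the within-stratum slope of change on baseline AFS and *v* the within-stratum variance of baseline AFS. Adding baseline reduces the residual variance from σ² to σ² − b²v. At *b* = 0 the second-look score rises one-for-one with baseline; at *b* = 1 it is unrelated to baseline.

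The documents give neither *b* nor *v*, and do not say whether 1.8 is a within-stratum or an overall SD. I assume four evenly spread whole-number scores per stratum, so *v* = (4² − 1)/12 = 1.25, and show both readings of the SD.

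**3. Reading A: 1.8 is the within-stratum SD.** Residual variance with baseline = 3.24 − 1.25b². Power is from the noncentral t, 69 per arm, difference 1. Stratum alone gives 90.0% throughout.

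| Slope *b* | Residual SD with baseline | Power with baseline | Shift of the stratum-only estimate for a 1.96-SE baseline imbalance |
|---|---|---|---|
| 0 | 1.800 | 90.0% | 0 |
| 0.25 | 1.778 | 90.7% | 0.09 |
| 0.5 | 1.711 | 92.6% | 0.19 |
| 0.75 | 1.593 | 95.6% | 0.28 |
| 1.0 | 1.411 | 98.5% | 0.37 |

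The SE of the baseline imbalance is √(2 × 1.25/69) = 0.190, so the shift is b × 1.96 × 0.190. This is not extra error: it is already inside the planned SE of 1.8 × √(2/69) = 0.306.

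At *b* = 0.5 the SE falls to 1.711 × √(2/69) = 0.291 and the 95% CI half-width from 1.978 × 0.306 = 0.61 to 1.978 × 0.291 = 0.58. The variance removed is 0.3125/3.24 = 9.6%, worth about 13 of the 138 evaluable patients. With *v* = 0.5 or 2.0 instead of 1.25, power at *b* = 0.5 is 91.1% or 94.1%.

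**4. Reading B: 1.8 is the overall SD.** Assume equal strata with means four points apart, so the between-stratum baseline variance is 2² = 4. Stratum-only residual variance = 3.24 − 4b²; with baseline, subtract a further 1.25b².

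| Slope *b* | Stratum only | Stratum plus baseline |
|---|---|---|
| 0.25 | variance 2.990, power 92.1% | variance 2.912, power 92.7% |
| 0.5 | variance 2.240, power 97.4% | variance 1.928, power 98.7% |
| 0.75 | above 99.9% | above 99.9% |

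Slopes above √(3.24/5.25) = 0.79 are impossible on this reading.

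**5. Validity of both models.** I simulated reading A with stratified 1:1 allocation, 138 patients, moderate 5 to 8 and severe 9 to 12 (assumed), half of patients severe, normal residuals and 5,000 trials per setting, at slopes from 0 to 1. Mean estimates were within 0.01 of the truth in both models. Type I error was 4.7% to 5.6% with stratum only and 5.1% to 5.7% with baseline added (Monte Carlo SE about 0.3 points). At slope 0 the average SE rose only from 0.306 to 0.307, which is the whole cost of the extra covariate.

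**The case against.** The strongest reply is that nothing here is an error. The stratum is the baseline AFS score in two categories, so the plan does adjust for baseline, coarsely, and it does so deliberately to match the randomisation. That stands.

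The sample size is also a plain two-group calculation with no stratum term, which arguably favours reading SD 1.8 as overall. The extra gain is then about 0.6 points of power at slope 0.25 and 1.3 at 0.5. Even on the within-stratum reading, a slope of 0.5 narrows the half-width by only 0.03 AFS points against a planned difference of 1. The 98.5% figure needs the extreme case in which second-look score is unrelated to baseline. All of this is fair, and every gain rests on undocumented inputs.

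Two further points are partly right. The general sentence on adjusting for severity can be read to cover the ordinal fallback; what is missing there is the continuous score. And an amendment to a primary model during a trial that is open label to the surgeon has to be documented as made without sight of results by arm.

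None of this gives a reason to leave the score out. A slope of exactly zero is also not the likeliest case. Entry starts at 5 and the planned mean changes are 5 and 6. If the score cannot fall below zero (an assumption; the documents do not print the scale), a patient who starts at 5 cannot improve by 6, so change is capped by baseline at the low end.

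**Conclusion.** The concern holds as a point of efficiency. The planned analysis is valid and the stated sample size stands. Leaving out the continuous pre-adhesiolysis score may give up some precision, by an amount the documents cannot settle. At slopes of 0.25 to 0.5, the gain in power is about 0.7 to 2.6 percentage points if SD 1.8 is within-stratum, and about 0.6 to 1.3 if it is overall. It is nil if change does not depend on baseline within strata, and larger only at steep slopes on the within-stratum reading. These figures assume 69 evaluable patients per arm, a true difference of 1, a within-stratum baseline variance of 1.25 and, for the overall reading, equal strata four points apart. The possible loss from adding the score is negligible.

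**What to change.** Amend the Statistical Analysis Plan before unblinding, and record that this was done without sight of results by arm:

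- Fit the primary ANCOVA with treatment, severity stratum and the continuous pre-adhesiolysis AFS score.
- Name the same covariates in the ordinal logistic fallback.
- Report the adjusted between-arm mean difference with its 95% CI, and keep the per-arm intervals as description. This is a reporting addition: the plan currently specifies intervals only within each arm.

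The cost is one degree of freedom, one reporting line and a documented amendment. No new data or patients are needed, and the sample size need not change. If results by arm have already been seen, keep the planned model as primary and present the baseline-adjusted model as a labelled sensitivity analysis.
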